#### 1.8.8 **Exploratory analyses**

All exploratory efficacy analyses for Treatment Period 2 will be performed by dosing group in the FAS-P90R and the FAS-P75R, separately. Exploratory analyses for Treatment Period 1 will be performed in the SAF-TP1. Analyses for Week 60 (rebound and relapse) will be based on the FUS.

### PASI and IGA mod 2011 0 or 1 response in Treatment Period 1

Summary statistics will be provided for absolute PASI scores in Treatment Period 1 as well as for absolute and percent change from baseline by visit.

Contingency tables for PASI 50/75/90/100 and IGA mod 2001 0 or 1 response in Treatment Period 1 will be presented by visit starting with Week 1 and will include absolute and relative frequencies.

#### DLQI, EQ-5D, WPAI-PSO and assessment of pain, itching and scaling in Treatment Period 1

For the DLQI subscale and the DLQI total score, the EQ-5D VAS and the EQ-5D utility index, for each of the main outcomes of the WPAI-PSO and for the assessment of pain, itching and scaling, the absolute and percentage change from baseline to week 4, 12 and 24 will be derived. Summary statistics will be provided for absolute values as well as for the percentage change by visit.

For the single EQ-5D dimensions contingency tables will be provided for each visit where the scale was to be assessed. Changes from baseline to each visit will be displayed using the categories *improved*, *unchanged* and *worsened* in each dimension.

#### Time to event analyses for PASI and IGA mod 2011 0 or 1 during Treatment Period 2

Kaplan-Meier analyses, log-rank tests and Cox proportional Hazard models will be performed for all time to event analyses in Treatment Period 2 with respect to the respective dosing groups in the analysis set. Further specifications of the applied statistical methods are provided in Section 2.3.

The analysis of time to PASI 90 response and the analysis of time to loss of PASI 75 response will be conducted in the FAS-P75R set, the analysis of time to loss of PASI 90 response in the FAS-P90R. The time to loss of IGA mod 2011 0 or 1 response will be performed in both patient sets for patients with IGA mod 2011 0 or 1 response at Week 24.

#### Body Surface Area affected by plaque-type psoriasis at Week 52

The absolute and percentage change from baseline to Week 52 will be derived. Summary statistics will be provided for absolute values as well as for the percentage change by visit for the FAS-P90R and the FAS-P75R.

#### Relapse and Rebound at Week 60

Contingency tables including absolute and relative frequencies will be provided for relapse and rebound at Week 60 in the FUS and in the PP-FUS. Risk differences including 95%-CIs between the (former) dosing groups, i.e. Group 3 vs. Group 4, will also be presented.

#### Association between PK data and PASI response during course of the study

# 1.8.9 These evaluations are not part of the current analysis plan. Resource utilization

Data relating to resource utilization might be used for the purpose of economic evaluations. However, these evaluations are not part of the current analysis plan.

#### 1.8.10 Pharmacokinetics

Analysis of pharmacokinetic (PK) data will be performed separately for Treatment period 1 and Treatment Period 2. All subjects from the respective Safety Set (SAF-TP1 and SAF-TP2) with quantifiable PK measurements of secukinumab will be included in the PK data analysis. Serum concentrations will be expressed in mass per volume units. All concentrations below the limit of quantification as well as missing data will be labeled as such in the concentration data listings. PK concentrations will be summarized by visit and, in Treatment Period 2, by treatment group. In addition to the overall summaries, PK concentrations will be provided by PASI response: in Treatment Period 1 the summary will be stratified by PASI response at Week 24 (PASI 90, PASI 75 to 90, below PASI 75), in Treatment Period 2 by PASI 90 response at Week 52. For the stratification by PASI response only subjects with a PASI assessment at Week 24 or Week 52, respectively, will be considered.

In addition to mean, standard deviation (SD), coefficient of variation (CV), median and quartiles, the geometric mean and geometric coefficient of variation (CV) and n(log) will be presented. The formula for deriving the geometric mean and CV (%) is as following:

- CV (%) = (SD/mean)\*100,
- geometric mean=exp( (sum of log transformed data) / number of non-missing data points after log transformation),
- geometric CV = sqrt( exp( variance of log-transformed data)-1)\*100.

In addition, sample number, concentration, sample date, sample time at pre-dose and minutes pre-dose will be listed by treatment sequence.

Values below lower limit of quantification/below detection limit will be imputed by 0.

Additionally, the geometric mean values during Treatment Period 1 will be displayed graphically stratified by PASI response at Week 24 (PASI 90, PASI 75 to 90, below PASI 75). Figures of the geometric means during Treatment Period 2 will be provided within each treatment group and stratified by PASI response at Week 52. For these figures only subjects with a PASI assessment at Week 24 or Week 52, respectively, will be considered.

#### 1.9 Standard safety evaluation

Safety analyses will be performed separately for Treatment Period 1, Treatment Period 2 and the Follow-Up period. Additionally, adverse events will be analyzed for the Entire Study Period combined (i.e. Treatment Period 1, Treatment Period 2).

Safety analyses for Treatment Period 1 will be based on the SAF-TP1, for Treatment Period 2 on the SAF-TP2, analyses for the post treatment Follow-Up period on the FUS and analyses for the Entire Treatment Period on the SAF-TP1.

#### Treatment groups for evaluation of Treatment Period 2

For safety-evaluations, the patient groups of PASI 90 responders and those who achieve PASI 75 but not PASI 90 will be pooled for Group 1 and Group 3; therefore, only 3 dosing groups will be analyzed in Treatment Period 2:

- Secukinumab 300 mg s.c. every 2 weeks (patients from Group 4).
- Secukinumab 300 mg s.c. every 4 weeks (patients from Group 1 pooled with Group 3).
- Secukinumab 300 mg s.c. every 6 weeks (patients from Group 2).

Additionally, the total number of patients over all groups will be analyzed in a separate column. Patients will be analyzed according to the treatment regimen they received.

If the treatment regimen of patients only deviates partially from the randomized treatment regimen during Treatment Period 2, these patients will be analyzed according to the treatment randomized.

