9.5.2 Safety variables

For safety-evaluations, the patient groups of PASI 90 responders and those who achieve PASI 75 but not PASI 90 will be pooled for Group 1 and Group 3; therefore, only 3 dosing groups will be compared:

- secukinumab 300 mg s.c. every 2 weeks (patients from Group 4).
- secukinumab 300 mg s.c. every 4 weeks (patients from Group 1 pooled with Group 3).

• secukinumab 300 mg s.c. every 6 weeks (patients from Group 2).

Patients will be analyzed according to the treatment they received.

Treatment emergent AEs (events started after the first dose of study drug or events present prior to the first dose of study drug but increased in severity based on preferred term) will be summarized. Only primary paths within MedDRA will be considered for AE reporting.

AEs will be summarized by presenting, for each treatment group, the number and percentage of patients

- having any AE,
- having an AE in each primary SOC and
- having each individual AE (preferred term).

Summaries will also be presented for AEs by severity and for study drug related AEs. If a patient reported more than one AE with the same preferred term, the AE with the greatest severity will be presented. If a patient reported more than one AE within the same primary SOC, the patient will be counted only once with the greatest severity at the SOC level, where applicable.

These summaries will be presented separately for study periods (Treatment Period 1, Treatment Period 2, Post-Treatment Follow-up Period), and for complete treatment periods (Treatment Periods 1 and 2 and Follow-up). Separate summaries will be provided for deaths, SAEs, other significant AEs leading to discontinuation and AEs leading to study drug discontinuation.

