#### Treatment groups for evaluation of Follow-Up Period

For the analysis of the post treatment Follow-Up Period Group 3 and Group 4 defined in Section 1.2 will be used next to a combined group.

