#### Treatment groups for evaluation of Entire Treatment Period

For the evaluation of the Entire Treatment Period all patients in the SAF-TP1 will be analyzed without consideration of any treatment groups.

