### 1.10 Compound specific safety evaluation

Safety topics of interest, such as risks defined in the Safety Profiling Plan, Risk Management Plan or topics of interest regarding signal detection or routine analysis are defined in the Program Case Retrieval Sheet that is stored in CREDI.

AEs of special interest (AESI) will be analyzed separately for Treatment Period 2 and the Entire Treatment Period. Crude incidence rates and corresponding confidence intervals of AESI will be summarized overall and by PT.

In addition, listings will be provided presenting which subjects experienced which risk.

The following AESI are part of the analysis.

- Major adverse cardiovascular events (MACE): identified per Novartis MedDRA Query (NMQ) "MACE (MI, Stroke, Cardiovascular death)"
- Inflammatory bowel disease: identified per NMQ "Inflammatory bowel disease"
- Candida infections: any AE with Candida high level term
- Malignancy: identified per NMQ "Malignant or unspecified tumours (excl. BCC and SCC)"
- Hypersensitivity and injection site reaction: identified per SMQ "Hypersensitivity"
- Hepatotoxicity: identified per SMQ "Drug related hepatic disorder severe events only"

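### The SAP leaves Follow-up out of the combined-period adverse-event analysis without declaring it, so adverse events of special interest starting after Week 52 have no special-interest count or confidence interval

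*SAP*

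**What the plan says.** Protocol section 9.5.2 sets out two layers of AE summary. The first is by period: "These summaries will be presented separately for study periods (Treatment Period 1, Treatment Period 2, Post-Treatment Follow-up Period". The second combines periods: "and for complete treatment periods (Treatment Periods 1 and 2 and Follow-up".

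SAP section 1.9 keeps the first layer: "Safety analyses will be performed separately for Treatment Period 1, Treatment Period 2 and the Follow-Up period". For Follow-up it works on the Follow-Up set (FUS), where "Group 3 and Group 4 defined in Section 1.2 will be used next to a combined group". The second layer is narrower than in the protocol: "adverse events will be analyzed for the Entire Study Period combined (i.e. Treatment Period 1, Treatment Period 2", with the bracket closing at that point. The SAP then calls this analysis the Entire Treatment Period and states that "all patients in the SAF-TP1 will be analyzed without consideration of any treatment groups".

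SAP section 1.10 adds an analysis of AESI: "AEs of special interest (AESI) will be analyzed separately for Treatment Period 2 and the Entire Treatment Period". It reports crude incidence with confidence intervals, overall and by preferred term, and adds listings by subject with no stated period limit.

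SAP section 1.1.1 declares two departures from the protocol's methods: body weight added to the key secondary model, and the pharmacokinetic response model dropped. The combined AE period is not mentioned.

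**The concern.** Two things follow from the text. First, the SAP narrows a safety summary that the protocol specifies and does not record the change. Second, the AESI tables inherit the narrower period, so they stop at Week 52.

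That matters because Follow-up is limited to Groups 3 and 4. Protocol section 3.2 explains that drug-free data after dosing up to every 4 weeks were already well reported, and section 3.3 says the 2-weekly regimen had not been tested in maintenance. Section 3.1 names safety as one purpose of the Week 60 visit. The AESI tables therefore omit a period kept partly to look at safety after the more intensive regimen. Group 3 is affected in the same way.

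**Working it through.** No figure in the documents is in dispute. The check is a comparison of text, with arithmetic only for scale.

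**Step 1: the combined period.**
- Protocol 9.5.2: Treatment Period 1 + Treatment Period 2 + Follow-up.
- SAP 1.9: Treatment Period 1 + Treatment Period 2.
- SAP 1.1.1: no such change declared.
- SAP 1.9.1: the treatment-emergent definition does include Follow-up.

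**Step 2: where an AESI starting after Week 52 can appear.** SAP 1.2 ends Treatment Period 2 at Week 52 and starts Follow-up after it. SAP 1.9.1 assigns an AE to a period by its start date.

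| Output | Covers onset after Week 52? |
|---|---|
| AESI table, Treatment Period 2 (SAP 1.10) | No |
| AESI table, Entire Treatment Period (SAP 1.10 with 1.9) | No |
| Follow-up AE tables by organ class and preferred term, Groups 3, 4 and combined (SAP 1.9, 1.9.1) | Yes |
| Summaries of deaths, serious AEs and liver-related AEs (SAP 1.9.1) | Yes, where applicable |
| AESI listings by subject (SAP 1.10) | Probably; no period limit stated |

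What is missing is the AESI grouping with its count and interval. Rows by preferred term do not supply it, because a query such as that for cardiovascular events or hypersensitivity gathers several terms and must count each patient once.

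**Step 3: size of the uncovered window.** The last dose is at Week 48 and Follow-up ends at Week 60.
- Weeks after the last dose: 60 − 48 = 12.
- In Treatment Period 2, so in an AESI table: 52 − 48 = 4.
- In no AESI table: 60 − 52 = 8, and 8/12 = 67%.

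**Step 4: patients and person-time.**
- Groups 3 and 4 (protocol 9.7.1): 1580 × 0.133 = 210.1, reproducing the stated 210, or 105 per group.
- Follow-up time in Group 4 if all 105 enter: 105 × 8 × 7 / 365.25 = 16.1 patient-years; for both groups, 32.2.

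**Step 5: chance of at least one uncounted Group 4 event.** The documents give no AESI rate, so the rates are assumed. Expected events = rate × 16.1; chance of at least one = 1 − exp(−expected).

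| Assumed rate per 100 patient-years | Expected events | Chance of at least one |
|---|---|---|
| 1 | 0.16 | 15% |
| 2 | 0.32 | 27.5% |
| 5 | 0.80 | 55% |
| 10 | 1.61 | 80% |

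**Step 6: weight in the pooled entire-period table**, on planned numbers with full completion.
- Treatment time: 1580 × 24 + (1140 + 210) × 28 = 37,920 + 37,800 = 75,720 patient-weeks.
- Follow-up time: 210 × 8 = 1,680 patient-weeks, and 1,680 / (75,720 + 1,680) = 2.2%.
- One further patient with an event there: 1/1580 = 0.06%.

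**The case against.** The strongest reply is that little is hidden. Follow-up AEs are tabulated by regimen with confidence intervals. Protocol section 7.2.1 treats every malignant neoplasm as serious, and Table 14-1 does the same for the severe drug-related hepatic query, so these events would also be in the serious-event summary. This stands. A reader might infer that AESI in Follow-up vanish from the report; the documents do not support that.

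A reader might also infer that the SAP breaks a protocol promise of AESI tables. It does not. Protocol section 9.5.2 promises the combined AE summary and no AESI table. The AESI analysis came in with SAP version 1.1, so its periods are the SAP's own choice.

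A third tempting reading is that AESI incidence is understated by a known amount, such as 8 of the 36 weeks after randomisation (22%), or one event in 105 patients (about 1 percentage point). Neither figure describes a planned AESI table. The entire-period analysis ignores regimen and has about 1580 planned patients. The Treatment Period 2 table covers the same planned 28 weeks in every group and is not biased by leaving out later drug-free time.

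Finally, a drafting slip is plausible: SAP section 1.9 uses two labels for the period, and the treatment-emergent definition includes Follow-up. That may explain the wording but does not correct it, since programmers will follow the stated definition.

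**Conclusion.** The point holds as a reporting and traceability gap. The SAP's combined AE period contradicts protocol section 9.5.2, and the change is undeclared. As a consequence of SAP sections 1.9 and 1.10 read together, an AESI starting after Week 52 in Groups 3 or 4 has no query-based count or confidence interval, although the event itself is reported elsewhere.

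The size is 8 drug-free weeks in about 210 planned patients, or 32.2 patient-years if all enter Follow-up. Whether any event falls there depends on rates the documents do not give; the 15% to 80% range for Group 4 rests on assumed rates of 1 to 10 per 100 patient-years. The primary and key secondary analyses are unaffected.

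**What to change.** 1. In SAP section 1.9, define the combined period as Treatment Period 1 + Treatment Period 2 + Follow-up, as in protocol section 9.5.2, and use one label for it throughout sections 1.9 and 1.10.
2. In SAP section 1.10, add an AESI table for the Follow-up period on the FUS, by Group 3, Group 4 and combined.

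Both steps are needed. The first restores the protocol's summary, but its results are pooled over all patients, so only the second shows events by regimen.

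The cost is two sentences and one table. The analysis sets, queries and interval method are already specified, and SAP section 1.1 already schedules the analysis after the last Week 60 visit. There is one small downside: in the pooled crude incidence, about 210 patients would be observed 8 weeks longer than the rest. A footnote can say so.

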For Group 3 and Group 4 at a minimum, patients will be contacted for safety evaluations during the 12 weeks following the last dose of study drug, including final contact at the 12-week point or the 30 days point following the last study visit (whichever is later). Documentation of attempts to contact the patient should be recorded in the patient's record.

Recommended order of assessments:

The recommended order of PRO assessment for completion by the patient is as follows:

- DLOI
- Patient's assessment of pain, itching and scaling

- EQ-5D[©] Health Status Questionnaire
- WPAI-PSO

The recommended order of efficacy and other assessments, which will be completed by the Investigator/qualified site staff, is as follows:

- IGA mod 2011 assessments (performed by the blinded assessor)
- PASI assessments (performed by the blinded assessor)
- Review PRO data (at applicable visits).
- Physical examination (at applicable visits).
- All remaining study visit procedures (eg vital signs measurements) are to be completed prior to study drug dosing
- Safety blood samples and PK blood sample will be collected
- Contact IRT to register the patient visit and enter all data as applicable.
- Self-administration of study medication. Note: if needed, a caregiver of the patient can be trained for home administration to provide support to the patient; corresponding training should be documented in the source data at the study center (see Section 5.5.4).

Table 6-1 Assessment schedule

Period	Scr		Treatment Period 1									Treatment Period 2								ita	Comments
Visit	1	2	3	4	5	6	7	8	9	10	11	12	13	14	15	16	17	18	19	d Vis	
Week	-4 to BL ^e	BL	1	2	3	4	8	12	16	20	24 a, b	28	32	36	40	44	48	52 c	60	Unscheduled Visit ^d	
Recommended visit window (days)			±2	±2	±2	±2	±5	±5	±5	±5	±2	±5	±5	±5	±5	±5	±5	±5	±5	Uns	
Informed consent	Χ																				
Demographics	Χ																				
Inclusion/exclusion criteria	X	x																			These assessments are supported by and stored within the source documentation. Data relating to inclusion/exclusion criteria are captured in the corresponding eCRF.
Smoking history	Χ																				
Psoriasis: medical history / previous psoriasis therapies	Х																				
Other medical history and prior medications	Х																				
Concomitant medications	Х	Х	Х	Х	Х	Х	Х	Х	Х	Х	Х	Х	Х	Х	Х	Х	Х	Х	Х	Х	
Physical examination	S	S	S	S	S	S	S	S	S	S	S	S	S	S	S	S	S	S	S	S	
Height	Χ																			X	
Weight	Χ	Χ									Χ							Х	Х	Χ	

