7.2.2 Serious adverse event reporting

To ensure patient safety, every SAE, regardless of causality, occurring after the patient has provided informed consent and until 30 days after the last study visit, or 12 weeks after the last study drug (if applicable), must be reported to Novartis within 24 hours of learning of its occurrence. Any SAEs experienced after this 30 day-period should only be reported to Novartis if the Investigator suspects a causal relationship to study drug.

Recurrent episodes, complications, or progression of the initial SAE must be reported as follow-up to the original episode, regardless of when the event occurs. This report must be submitted within 24 hours of the Investigator receiving the follow-up information. An SAE that is considered completely unrelated to a previously reported one should be reported separately as a new event.

Information about all SAEs (either initial or follow-up information) is collected and recorded in English on the paper SAE Report Form or the electronic SAE Form within the data capture

Protocol No. CAIN457A3302

system (where available). The Investigator must assess the relationship to each specific component of the study drug (if the study drug consists of several components).

SAEs (initial and follow-up) that are recorded *electronically* in the eCRF system (if this function is available) should be entered, saved and e-signed within 24 hours of awareness of the SAE or changes to an existing SAE. These data will automatically be submitted to Novartis Drug Safety and Epidemiology immediately after Investigator signature or 24 hours after entry, whichever occurs first.

Follow- up information provided should describe whether the event has resolved or continues, if and how it was treated, whether the treatment code was broken or not and whether the patient continued or withdrew from study participation. Each re-occurrence, complication, or progression of the original event should be reported as a follow-up to that event regardless of when it occurs.

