### 1.2 Subjects and treatments

The following study periods will be considered for the analysis:

- Screening Period (Screening to Visit 2 [=Baseline], excluding Visit 2 [=Baseline])
- **Treatment Period 1** (Visit 2 [=Baseline] to Week 24 pre-dose)
- Treatment Period 2 (Week 24 post-dose to Week 52)
- Follow-Up Period (Week 52 to Week 60, excluding Week 52).

For Treatment Period 1 (Baseline to Week 24) all patients will receive the same treatment:

• Secukinumab 300 mg s.c. will be self-administered at Baseline, weekly at Week 1, Week 2 and Week 3 and every 4 weeks thereafter (i.e., Week 4, 8, 12, 16 and 20).

At Week 24, all patients will be assessed in term of PASI response and either randomized to one of the 4 treatment groups in Treatment Period 2 (Week 24 to Week 52) or withdrawn from the study. Randomization is stratified by body weight at this visit ("body weight  $\geq 90 \text{ kg}$ " vs. "body weight < 90 kg" at Week 24) in order to ensure balanced allocation of patients to treatment groups within the weight strata.

Patients with at least a 90% reduction in PASI score from Baseline will be randomized at Week 24 on a 1:1 basis to Group 1 or Group 2:

- **Group 1** (recommended maintenance treatment): secukinumab 300 mg s.c. every 4 weeks (Week 24, 28, 32, 36, 40, 44 and 48).
- **Group 2** (experimental dosing maintenance treatment): secukinumab 300 mg s.c. every 6 weeks (Week 24, 30, 36, 42 and 48).

Patients with less than 90% reduction in PASI score from Baseline at Week 24 but who achieved at least a 75% reduction in PASI score from Baseline are eligible for dose frequency intensification and will be randomized on a 1:1 basis to either Group 3 or Group 4:

- **Group 3** (recommended maintenance treatment): secukinumab s.c. 300 mg every 4 weeks (Week 24, 28, 32, 36, 40, 44 and 48).
- **Group 4** (experimental maintenance treatment): secukinumab s.c. 300 mg every 2 weeks (Week 24, 26, 28, 30, 32, 34, 36, 38, 40, 42, 44, 46 and 48).

Patients with a reduction in PASI score from Baseline of less than 75% at Week 24 are not eligible for randomization and are discontinued from the study.

The following analysis sets will be used for the data analysis.

Safety set for Treatment Period 1 (SAF-TP1): The safety set for Treatment Period 1 includes all subjects who took at least one dose of study treatment during this treatment period.

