**Safety set for Maintenance Treatment Period 2 (SAF-TP2)**: The SAF-TP2 includes all patients who were randomized and received at least one dose of study drug at or after the Week 24 visit. Subjects will be analyzed according to treatment received.

Full analysis set for Treatment Period 2 of PASI 90 Responders (FAS-P90R): The FAS-P90R will include all patients who were rated as PASI 90 responders at the Week 24 visit, randomized to treatment groups 1 or 2 and received at least one dose of study drug at or after visit Week 24.

Full analysis set for Treatment Period 2 of PASI 75 Responders who do not achieve a PASI 90 Response (FAS-P75R): The FAS-P75R will include all patients who were rated as PASI 75 responders but do not achieve a PASI 90 response at the Week 24 visit, were randomized to treatment groups 3 or 4 and who received at least one dose of study drug at or after visit Week 24.

**Per-Protocol Set for Treatment Period 2 of PASI 90 Responders (PP-P90R): The PP-P90R** will include all patients from the FAS-P90R who complete the study as scheduled without any major deviations from the protocol which may affect the primary outcome of this study. Major deviations will be based on selected protocol deviations as defined in the Data Review Plan and additional criteria which might have impact on the treatment's efficacy. The final classifications of deviations as major (i.e. leading to withdrawal from the PP-P90R) will be performed in a data review before start of the analysis.

**Follow-Up set (FUS):** all patients from dosing group 3 or 4 who entered the Follow-Up (FU) Period of the study, i.e. who continue into the next phase of the trial at Week 52 and for whom any efficacy or safety data from the FU Period are available.

**Per-Protocol Follow-Up set (PP-FUS):** all patients from the FUS without any major deviations from the protocol in the follow-up period which may affect the rebound assessment at the end of this period. The final classifications of deviations as major (i.e. leading to withdrawal from the PP-FUS) will be performed in a data review before start of the analysis.

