#### 1.4.3 Screening, baseline and post-baseline definitions

Screening refers to any procedures (e.g., checking inclusion and exclusion criteria) performed prior to the date of visit 2. Per protocol, subject informed consent must be obtained prior to performing any study related activity. The date of signing informed consent is the start date of screening period. Any assessment obtained during the screening period will be labeled screening assessment.

Visit 2 is defined as *Baseline* visit. All consecutive visits are labeled according to the preplanned study week where they occur, i.e. Week 1, Week 2, and so on.

Week 24 is defined as the end of Treatment Period 1 (visit 11) for patients without premature discontinuation during Treatment Period 1. For patients with premature termination within Treatment Period 1 the last visit is defined as end of Treatment Period 1.

Week 52 is defined as the end of Treatment Period 2 (visit 18) for patients without premature discontinuation during Treatment Period 2. For patients with premature termination in Treatment Period 2 the last visit is defined as end of Treatment Period 2.

Any visits and assessments occurring after the end of Treatment Period 2 visit (Week 52 in the eCRF) will be aligned to the Week 60 Follow-Up visit.

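### Deaths and SAEs that start after the last visit in Groups 1 and 2 are collected but assigned to no SAP safety table

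*SAP*

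**What the plan says.** **Collection.** Protocol 7.2.2 requires every SAE, whatever its cause, from consent "until 30 days after the last study visit, or 12 weeks after the last study drug (if applicable), must be reported to Novartis". The next sentence reads "Any SAEs experienced after this 30 day-period should only be reported to Novartis if the Investigator suspects a causal relationship to study drug". Protocol Section 6 (visit windows) sets a safety-contact rule for Groups 3 and 4 that takes the later of 12 weeks after the last dose and 30 days after the last visit. It gives no such rule for other patients.

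**Periods.** SAP 1.2 ends Treatment Period 1 at Week 24 pre-dose, Treatment Period 2 at Week 52 and the Follow-Up Period at Week 60. For early stoppers, SAP 1.4.3 states "For patients with premature termination in Treatment Period 2 the last visit is defined as end of Treatment Period 2", with a parallel rule for Treatment Period 1. SAP 1.9.1 allocates an AE to a period by its start date and gives no lag window after the last visit or dose.

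**Sets.** SAP 1.9 bases "analyses for the post treatment Follow-Up period on the FUS and analyses for the Entire Treatment Period on the SAF-TP1". SAP 1.2 defines the FUS as "all patients from dosing group 3 or 4 who entered the Follow-Up (FU) Period of the study". SAP 1.9 defines the combined AE analysis as Treatment Periods 1 and 2.

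**What the protocol planned.** Protocol 9.5.2 describes a combined AE summary over both treatment periods and Follow-up. SAP 1.1.1, which lists departures from the protocol's methods, does not mention that Follow-up was dropped.

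**The concern.** The collection rule runs past the last visit for everyone. The tabulation rule runs past it only for Groups 3 and 4. A programmer who follows the SAP literally would have a reported death or SAE in Group 1 on, say, Day 380 and nowhere to put it: Treatment Period 2 has closed, the patient is not in the FUS, and the combined period has also ended.

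What is at stake is the completeness of the death and SAE counts by dosing interval, including serious events of special interest. SAP 1.10 analyses special-interest events only for Treatment Period 2 and the entire treatment period. Because the combined period leaves out Follow-up, special-interest events in Groups 3 and 4 between Weeks 52 and 60 also miss those tables. The primary efficacy result is not affected.

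**Working it through.** **Inputs.** Study day = 7 × week + 1 (SAP Table 1-3: Week 48 = Day 337, Week 52 = Day 365). Groups 1 and 2: 1140 planned (Protocol 9.7). Groups 3 and 4: 13.3% of 1580 (Protocol 9.7.1). Below PASI 75 at Week 24: 5.9% + 6.5% = 12.4% (Protocol 3.2).

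**The plan's own figures first.** Week 60 = 7 × 60 + 1 = Day 421, and 421 − 337 = 84 days = 12 weeks, as Protocol 3.1 states. 0.133 × 1580 = 210, as stated.

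**Where collection and tabulation end, for patients who attend as scheduled:**

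| Patients | Last dose / last visit | SAP period closes | 30 days after visit | 12 weeks after dose | Table for a later event |
|---|---|---|---|---|---|
| Groups 1, 2 | Day 337 / 365 | Day 365 | Day 395 | Day 421 | None |
| Not randomised | Day 141 / 169 | Day 169 | Day 199 | Day 225 | None, unless the combined table is read by calendar time |
| Groups 3, 4 | Day 337 / 421 | Day 421 | Day 451 (Week 64.3) | Day 421 | None after Day 421 |

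**Early stoppers.** Protocol 5.5.10 and Section 6 place their end-of-treatment visit at least 28 days after the last dose, and the SAP ends their period at the last visit. With the visit at 28 days, the two candidate collection limits are 28 + 30 = 58 and 84 days after the last dose. The 30-day limit becomes the later one once the visit is more than 84 − 30 = 54 days after the last dose.

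**Exposure in the untabulated window (30 days per patient):**
- Groups 1 and 2: 1140 × 30 / 365.25 = 93.6 patient-years.
- Not randomised: 0.124 × 1580 = 196 patients; 196 × 30 / 365.25 = 16.1 patient-years.
- Groups 3 and 4 after Week 60: 210 × 30 / 365.25 = 17.2 patient-years.

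**Events, at an assumed 5 to 10 SAEs per 100 patient-years (not from the documents):**
- Groups 1 and 2: 93.6 × 0.05 to 0.10 = 4.7 to 9.4.
- Not randomised: 0.8 to 1.6.
- Groups 3 and 4 after Week 60: 0.9 to 1.7.

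**Scale.** Treatment Period 2 for all 1350 planned randomised patients is 1350 × 28/52 = 727 patient-years, or 36 to 73 SAEs at the same rates. At a constant rate, the 30-day window in Groups 1 and 2 is 30/196 = 15% of their Treatment Period 2 time.

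**Ambiguity in the collection limit.** For a Group 1 or 2 completer the candidate dates are 421 − 395 = 26 days apart. For a Group 3 or 4 completer they are 451 − 421 = 30 days apart, in the opposite order.

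**The case against.** Four objections have force.

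- **The gap is partly an inference from silence.** The treatment-emergent definition in SAP 1.9.1 has no upper limit for new events, and its promised summaries of deaths and SAEs name no period. The combined table uses every treated patient, so on a calendar reading it could take an event dated between Weeks 24 and 52 in a patient who was not randomised or who stopped in Treatment Period 1. This stands for those patients. It does not help Groups 1 and 2 after Week 52, because the combined period ends there. SAP 1.4.3 does align later visits and assessments to Week 60, but the follow-up tables use the FUS, which excludes these groups.
- **A reader might infer that the protocol contradicts itself on when SAE collection ends.** The documents do not show that. If the words in brackets in Protocol 7.2.2 restrict the 12-week limit to Groups 3 and 4, that section and Section 6 can be read together: the later date for those groups, 30 days for everyone else. The text does not say this, so the point is unresolved rather than contradictory.
- **A reader might infer that follow-up differs by group for no reason, or that the event behind an early stop is lost.** Neither is supported. Protocol 3.2 explains that treatment-free follow-up data up to the 4-weekly exposure already exist. An event that leads to stopping is counted by its start date, and at least four weeks off drug fall inside an early stopper's period if the required visit takes place. Group 3 and 4 stoppers may also return at Week 60, although the FUS wording about continuing at Week 52 leaves their membership unclear.
- **The numbers are small.** This is fair. The rate is assumed, and the events are split over two equal arms.

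**Conclusion.** The tabulation gap stands for Groups 1 and 2. Under the SAP's stated periods and sets, deaths and SAEs that start after the last visit are collected for at least 30 days and enter no summary. That covers 1140 of 1580 planned patients (72%) and about 94 patient-years. The period definitions establish the gap whatever the event rate; the figure of 5 to 9 events depends on the assumed rate.

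The gap probably extends to patients not randomised at Week 24 and to Treatment Period 1 stoppers, subject to the calendar reading above. It also covers Group 3 and 4 SAEs from Week 60 to about Week 64 where the 30-day limit applies. It would be wrong to claim that all early stoppers' events are lost, or that the documents show these events occur at meaningful drug levels; they give no half-life for secukinumab.

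The unlisted removal of Follow-up from the combined summary is a plain difference between SAP 1.9 and Protocol 9.5.2. The end of SAE collection is a separate, lesser ambiguity of 26 to 30 days for patients who attend as scheduled.

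**What to change.** **SAP 1.2 and 1.9**
- Extend the combined summary of deaths and SAEs on the SAF-TP1, including serious special-interest events, to the end of SAE collection.
- Show events that start after the last visit on a separate line, by dosing group or as not randomised.
- Restore Follow-up to the combined period as in Protocol 9.5.2, or list its removal in SAP 1.1.1 with a reason.
- Keep non-serious special-interest events within the full AE collection period. Protocol 7.2.2 extends collection for SAEs only, and a longer window would mix complete and serious-only ascertainment.

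**Protocol 7.2.2 and Section 6**
- Reconcile the two sentences of 7.2.2 with each other and with the Group 3 and 4 contact rule, so that the end of SAE collection is explicit for each group. Protocol 11.1 requires a written amendment for this. Which date applies is for the sponsor to settle.

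**Cost.** The SAP part needs one derived date, one table line and a little programming, and a few more SAEs will appear in the report. The protocol part carries the usual approvals for an amendment.
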